1.0 Background

Tobacco smoking is the leading preventable cause of disease and death in the US and the world. Every year smoking kills nearly half a million Americans¹ and costs the nation 1.6% of the GDP.² As of 2013, 18% of U.S. adults smoke,³ and the prevalence is even higher in vulnerable groups such as minorities. Furthermore, African-American smokers smoke fewer cigarettes than white Americans, yet have disproportionally higher rates of smoking-related diseases.⁴ In all smokers, most quit attempts fail, and members of minority groups are even less likely to succeed,⁵ despite using FDA-approved pharmacotherapy.

Nicotine mediates its addictive effects in the brain, where it binds to CNS receptors, including nicotinic acetylcholine receptors (nAChRs).⁶ Nicotine undergoes rapid (half-life ~two hours) and extensive hepatic metabolism to cotinine, primarily by the enzyme CYP2A6.⁷ Cotinine, in turn, is further metabolized to 3-hydroxycotinine exclusively by hepatic CYP2A6.⁶ Genetic variation in pathways related to nicotine metabolism, primarily *CYP2A6*, have been associated with smoking related traits, including cigarette consumption,⁸⁻¹⁰ and response to treatment.¹¹

The ratio of 3-hydroxycotinine to cotinine, known as the nicotine metabolite ratio, or NMR, is a geneticallyinformed biomarker reflecting CYP2A6 activity and the rate of nicotine metabolism.¹² A recent RCT in *Lancet Respiratory Medicine* found that the NMR can be used to individualize treatment for smokers.¹³ Specifically, subjects who were identified as "fast" metabolizers (as opposed to "slow" metabolizers) demonstrated a twofold improvement in cessation rates when treated with varenicline compared to nicotine replacement therapy (NRT). As a genetically-informed biomarker, NMR has been suggested as the tool of choice because it is inexpensive and has a relatively quick turnaround, lending feasibility to its role in guiding initial choice of pharmacotherapy. However, it is currently unknown whether a nicotine metabolism-guided approach utilizing NMR would be effective in a real world clinical environment.

2.0 Rationale and Specific Aims

Without the use of proven quit aids, rates of smoking cessation are exceedingly low, with only 5-10% of smokers able to quit for 6 months or more.¹⁴ Approved drugs, including bupropion, NRT (i.e., patch, gum, lozenge, nasal spray, and inhalers), and varenicline, have each been shown to dramatically improve quit rates compared to placebo,¹⁵⁻¹⁸ and current guidelines do not preferentially recommend any agent as first line therapy.¹⁸ While this standard guideline-based approach does result in a 1.5 to 3-fold increase in success compared to placebo, the absolute rates of smoking cessation remain low. At one year, a quarter or less of smokers who use proven behavior therapy and pharmacotherapy remain abstinent.¹⁹ A precision medicine approach utilizing NMR to tailor pharmacologic treatment is promising but unproven to increase quit rates and reduce smoking-related diseases.

Our overarching hypothesis is that tailored smoking cessation therapy, guided by NMR, results in higher rates of tobacco cessation compared to usual care. However, there are important challenges to be addressed prior to conducting a full-scale randomized controlled trial (RCT) comparing tailored treatment to usual care. We must establish that sufficient numbers of subjects can be enrolled; procedures for specimen collection, processing, and data analysis must be in place; and patient attitudes should be determined and considered in the study design.

The goal of this pilot project is to create infrastructure, establish feasibility, and provide necessary preliminary data to design and conduct a prospective randomized trial comparing tailored smoking cessation treatment to usual care. To accomplish this, we will enroll up to 50 outpatient smokers from the Vanderbilt Heart and Vascular Institute (VHVI). After consent, subjects will complete questionnaires, provide biologic samples, and have nicotine metabolic status determined (nicotine metabolic ratio (NMR)). Subjects will be assigned to either: 1) usual care for smoking cessation or 2) personalized smoking cessation care which incorporates the NMR. Biochemically confirmed abstinence (by exhaled carbon monoxide, using a threshold of < 10 parts per million (ppm)) will be determined at the six month follow up.²⁰ For deliverables, we will: 1) demonstrate capacity to conduct large-scale personalized smoking cessation trials in the clinical environment, and 2) assess patient attitudes regarding personalized smoking treatment.

Aim 1. Develop infrastructure and procedures necessary to conduct a prospective randomized trial comparing tailored smoking cessation treatment to usual care. We hypothesize that we will successfully: 1) enroll outpatient adult daily smokers; 2) collect, process, and store relevant biologic samples; 3) conduct follow-up assessments and accurately ascertain pertinent smoking cessation and patient reported outcome measures.

Aim 2. Assess patient attitudes regarding personalized smoking therapy including: 1) interest in receiving personalized information, and 2) willingness to guide therapy based on personalized data. We hypothesize that a majority (>50%) of subjects will: 1) favorably view receiving personalized smoking information, and 2) express willingness to guide therapy based on personalized data.

3.0 Animal Studies and Previous Human Studies

Our group has not performed prior animal or human studies related to NMR. However, a recently published RCT in humans reported NMR can be used to guide smoking cessation therapy.¹³

4.0 Inclusion/Exclusion Criteria

Inclusion criteria: Eligible subjects include adult (18 years of age or older) daily smokers who are seen in VHVI outpatient clinic or cardiology inpatients admitted to VUMC. Current smoking is defined as smoking, on average, ≥5 cigarettes per day every day in the month prior to enrollment. Potential subjects must agree to participate and be willing to accept a medication prescription for tobacco cessation. Subjects must be eligible (i.e., no medical contraindications and willing to take) to receive at least two out of three FDA-approved smoking cessation medications (bupropion, varenicline, and NRT). The requirement of eligibility to take at least 2 of 3 FDA approved medications is necessary for this study so that individuals can take advantage of the NMR-driven guidance of a nicotine medication (i.e., NRT for slow metabolizers) vs. a non-nicotine medication (i.e., varenicline or bupropion for fast/normal metabolizers).

Exclusion criteria: In addition to medication contraindications, subjects will be excluded for inability to give informed consent or participate due to serious psychiatric (e.g., psychosis, schizophrenia, hospitalization for psychiatric condition in the past 3 months or change in psychiatric medications in the past 3 months) or cognitive disorder (e.g., dementia, severe mental retardation); receiving palliative or hospice care; pregnant or breastfeeding; no access to a telephone or inability to communicate by telephone; unable to speak and read English. Because levels of nicotine metabolites fall below detection over time we will exclude patients who have been completely abstinent from cigarettes for >3 days.

In order to maximize participant safety, eligibility for medications will be reviewed by three separate members of the study team. Initial screening will be conducted by the study RA at the time of enrollment. Between enrollment and intervention phone call (~1 week) medication eligibility will be reviewed for each participant by the study PI [name] using a detailed chart review. Finally, at the time of intervention phone call, medication eligibility will again be confirmed by the study counsellor, who is a trained smoking counsellor and nurse (RN).

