As described above, subject samples will be processed through ARUP Laboratory as they would for standard clinical care. Results are available within 2-5 days from the time of blood draw. Slow metabolizers will be defined by a NMR <0.31 and fast metabolizers will be defined by a NMR \geq 0.31 .¹³ Once available, subject NMR values will be entered into the study's secure REDCap database by study personnel.

Study Intervention, medication provision and blinding

Medication Costs

All medications accepted by participants at the initial intervention phone call will be provided to participants free of charge. Medications may be shipped to patients free of charge where appropriate. Subjects in the usual care arm who are still smoking at 6 months will have an opportunity to receive a prescription for smoking cessation therapy at the end of study (see below). Participants who wish to receive prescriptions at that point will be responsible for the cost of medications.

Usual Care Group

All subjects, including those assigned to usual care, will receive phone calls from clinical personnel within 1 month of enrollment. In order to minimize inconvenience, subjects will be asked their preferred times to be called at the time of enrollment. With the aid of a written script, staff will provide participants a verbal description of smoking cessation medications they are eligible to take (as determined by study physician), including efficacy and common side effects. If subjects would like to take a smoking cessation medication, they will be allowed to choose from those they are medically able to receive, and the study physician will call in a prescription to an outpatient pharmacy (with which arrangements have been made to have medication costs billed to the study rather than the subject). Regardless of whether subjects choose to receive a prescription for a medication, they will be offered referral to their state Tobacco Quit Line for smoking cessation counselling via an online portal. This portal will track the patient's progress through the quit line process and these data may be collected for research purposes. Verbal instructions will be provided to participants given prescriptions to contact their primary provider and the research study staff (during regular business hours) in case of adverse effects of a medication. They will also be instructed to call 911 if they believe they are having a medical emergency.

Personalized Care Group

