All subjects, including those assigned to personalized care, will receive phone calls from clinical personnel within 1 month of enrollment. In order to minimize inconvenience, subjects will be asked their preferred times to be called at the time of enrollment. Staff contacting subjects in the personalized care group will have access to NMR values when they become available in the study's secure REDCap database. With the aid of a written script, staff will provide participants a personalized (based on NMR) verbal description of smoking cessation medications they are eligible to take (as determined by study physician), including efficacy and common side effects. If subjects would like to take a smoking cessation medication, they will be allowed to choose from those they are medically able to receive, and the study physician will call a prescription into an outpatient pharmacy (with which arrangements have been made to have medication costs billed to the study rather than the subject). Regardless of whether subjects choose to receive a prescription for a medication, they will be offered referral to their state Tobacco Quit Line for smoking cessation counselling via an online portal. This portal will track the patient's progress through the quit line process and these data may be collected for research purposes. Verbal instructions will be provided to participants given prescriptions to contact their primary provider and the research study staff (during regular business hours) in case of adverse effects of a medication. They will also be instructed to call 911 if they believe they are having a medical emergency.

Follow up phone calls

Study RAs will call subjects at approximately 1, 3 and 6 months post-intervention phone call to assess smoking behavior, self-reported adherence, and side effects including neuropsychiatric side effects. Study personnel will make up to 10 calls per follow up at different times of day and days of the week and call subjects' alternate contacts when needed. Participants will receive \$10 for each phone call that they complete.

Single arm crossover for subjects in Usual Care Group

Subjects in the Usual Care Group who are still smoking at 6 month follow up will receive an additional intervention from study staff. With the aid of a written script, staff will provide participants a

	Baseline	1 mo*	3 mo*	6 mo*	2 weeks*
Outcomes					
Demographics	Х				
Smoking behavior	Х	Х	Х	X	Х
Side effect screening	Х	Х	Х		

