Adverse drugs reactions: Subjects in this study will receive one of three FDA-approved smoking cessation therapies (NRT, varenicline, or bupropion) and will have the potential to experience drug-related side effects. Nicotine replacement therapy is generally very safe (it is sold over the counter). However, possible side effects include skin irritation or itching (patch), dizziness, headache, nausea, and rapid heartbeat. Common side effects of varenicline include nausea, sleep disturbance and vivid dreams, gastrointestinal symptoms, and vomiting. Very rarely, patients, particularly those with unstable psychiatric conditions, may experience symptoms such as behavioral changes, agitation, depressed mood, and suicidal behavior during varenicline treatment. Common side effects of bupropion include dry mouth, irritability, and difficulty sleeping. A large trial of over 8000 patients was presented at the Society for Research on Nicotine and Tobacco in Chicago in March, 2016, and did not demonstrate any difference in neuropsychiatric symptoms (including suicidal ideation and suicidal behavior) between patients on varenicline, bupropion, or nicotine replacement therapy (EAGLES; ClinicalTrials.gov Identifier: NCT01456936). Very rarely, patients can have seizures, especially in those with a history of seizures. To protect against risk from pharmacotherapy usage, this study will only use FDA-approved smoking cessation medications and tobacco treatment providers will screen patients to identify contraindications to NRT, bupropion or varenicline. Written and verbal instructions will be provided to patients given medication to contact their primary physician and the research PI, [name], in case of adverse effects of a medication. Additionally, RAs will call subjects at regular intervals (as described above) to monitor for serious side effects including neuropsychiatric side effects. Study personnel will make up to 10 calls per week at different times of day and days of the week and call subjects' alternate contacts when needed. Ultimately, the PI ([name]) will review any serious adverse events and report them appropriately to the IRB.

8.0 Reporting of Adverse Events or Unanticipated Problems Involving Risk to Participants or Others Any adverse events will be reported to the IRB according to IRB policies and procedures.

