10.0 Statistical Considerations

This pilot project is intended to create infrastructure, establish feasibility, and provide necessary preliminary data to design and conduct a prospective RCT comparing tailored smoking cessation treatment to usual care. As such, we are not powered to detect differences between treatment groups in regards to primary or secondary outcomes. However, we will conduct descriptive and exploratory analyses of collected data as well as assess for between-group differences.

Aim 1. Develop infrastructure and procedures necessary to conduct a prospective randomized trial

comparing tailored smoking cessation treatment to usual care.

Hypothesis: We hypothesize that we will successfully: 1) enroll adult daily smokers from an outpatient clinic; 2) collect, process, store, and analyze relevant biologic samples; and 3) conduct follow-up assessments and accurately ascertain pertinent smoking cessation and patient care outcome measures.

Primary analysis: As a primary analysis, for each group we will calculate descriptive statistics for relevant demographic and clinical parameters, rates of enrollment and loss to follow-up, smoking cessation, and side effects. These data will be critical to inform future prospective studies.

Aim 2. Assess patient attitudes regarding personalized smoking therapy including: 1) interest in receiving personalized information, and 2) willingness to guide therapy based on personalized data. Hypothesis: A majority (>50%) of subjects will: 1) favorably view receiving personalized smoking information; and 2) express willingness to guide therapy based on personalized data.

Primary analysis: As a primary analysis, we will calculate the proportion of subjects that provided favorable responses (4 or 5 on Likert Scale) for questions addressing: 1) willingness to receive patient-specific smoking data; and 2) willingness to use these data to guide therapy, as reflected by the % who fill the prescription that is recommended by the NMR test results. We will also calculate rates of self-reported adherence, use of the quit line, and cessation at each follow up.

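### The rule requiring eligibility for two of three medications does not secure a nicotine and a non-nicotine option, which is its stated purpose: varenicline plus bupropion also qualifies

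*Protocol*

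**What the plan says.** Section 4.0 (Inclusion criteria) sets the rule: "Subjects must be eligible (i.e., no medical contraindications and willing to take) to receive at least two out of three FDA-approved smoking cessation medications". The three are bupropion, varenicline and NRT. The next sentence gives the reason: the rule is needed so that "individuals can take advantage of the NMR-driven guidance of a nicotine medication (i.e., NRT for slow metabolizers) vs. a non-nicotine medication", the latter being varenicline or bupropion for fast or normal metabolizers. NRT is therefore the only nicotine medication in the set.

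The exclusion criteria in the same section open with "In addition to medication contraindications, subjects will be excluded for inability to give informed consent".

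Section 6.0 describes the intervention call. In the personalized arm, staff give an NMR-based "verbal description of smoking cessation medications they are eligible to take (as determined by study physician"). In both arms, subjects who want a medication are told of their options and "they will be allowed to choose from those they are medically able to receive".

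Section 10.0 (Aim 2, primary analysis) measures willingness to use personalized data to guide therapy "as reflected by the % who fill the prescription that is recommended by the NMR test results".

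**The concern.** The criterion counts medications, while its stated reason concerns classes of medication. A screener who follows the text exactly can enrol a subject for whom the reason cannot be met: someone with a medical contraindication to NRT who can take both varenicline and bupropion. Whatever that subject's NMR, only the non-nicotine class is open.

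What is at stake is the fill measure in Aim 2. It is meant to show whether subjects let the NMR guide their treatment. A subject with one class available cannot show this, but is still counted. Aim 1 and the Likert items of Aim 2 are not affected. The crossover after 6 months is also outside the point, because section 6.0 gives its intent as studying medication uptake. Subjects who could take NRT but decline it are outside it too.

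**Working it through.** The plan states no figure to reproduce here, so the check has three parts.

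**1. Which sets satisfy the rule.** All sets of two or more from the three medications in section 4.0:

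| Available set | Nicotine option | Non-nicotine option | Meets stated reason |
|---|---|---|---|
| NRT + varenicline | yes | yes | yes |
| NRT + bupropion | yes | yes | yes |
| NRT + varenicline + bupropion | yes | yes | yes |
| varenicline + bupropion | no | yes | no |

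Three of the four sets meet the reason. A non-nicotine option is always present, so the gap runs in one direction only.

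**2. Whether another provision closes the gap.**
- The three-step eligibility review in section 4.0 checks medication eligibility but adds no requirement by class.
- The opening words of the exclusion criteria could be read as excluding anyone with any medication contraindication. All three drugs would then be medically open to every subject. That reading conflicts with section 6.0, which limits the choice to what each subject can medically receive, and it would leave the two-of-three allowance with no medical use.
- No other section requires NRT to be one of the two.

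**3. Effect on the Aim 2 fill proportion.** Take a subject without NRT in the personalized arm.
- Slow metabolizer (NMR <0.31, section 6.0), recommendation taken to be NRT: the subject cannot fill it and counts as unwilling.
- Slow metabolizer, recommendation confined to medications the subject is eligible for: any fill counts as agreement.
- Fast metabolizer: any fill counts as agreement.

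In none of these does the result show that the NMR steered the class. The protocol does not say which reading applies to the slow metabolizer.

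Size, with n = 25 in the personalized arm. This assumes the maximum enrolment of 50 and equal allocation; section 5.0 states blocks of 10 but no ratio. Let x be the number counted as filling. Leaving one such subject out changes the proportion as follows:
- Subject counted as a non-filler: x/24 − x/25 = x/600, at most 24/600 = 4.0 points.
- Subject counted as a filler: (x − 1)/24 − x/25 = (x − 25)/600, at most 24/600 = 4.0 points in size (at x = 1).

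| x of 25 | Proportion | Filler left out | Non-filler left out |
|---|---|---|---|
| 12 | 48.0% | – | 12/24 = 50.0% |
| 13 | 52.0% | 12/24 = 50.0% | 13/24 = 54.2% |
| 14 | 56.0% | 13/24 = 54.2% | 14/24 = 58.3% |

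The Aim 2 hypothesis is a proportion above 50%. One such subject changes that reading only at 13 of 25.

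The share m of subjects medically unable to take NRT is not in the protocol. With P(at least one of 25) = 1 − (1 − m)^25:
- m = 1%: 22%
- m = 2%: 40%
- m = 5%: 72%

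These values of m are assumptions. They cover any subject without NRT; the blocked case also needs a slow metabolizer and is rarer.

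For comparison, the 95% sampling margin at 50% is 1.96 × √(0.25/25) = 0.196, or about ±20 points.

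**The case against.** The strongest reply is that section 4.0 calls the rule necessary, not sufficient. Having both classes does require at least two of the three medications, so read literally the sentence is true. That is right as logic, but the sentence goes on to say what the rule is for, and no other provision supplies the missing part.

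A second reply is that the description at the intervention call is already limited to medications the subject is eligible for, so recommending a contraindicated drug is the less likely reading. This has force, but section 10.0 does not define the recommendation. Under the more likely reading, any fill counts as agreement, which is no more informative about class. Such a subject does still inform uptake, because filling nothing remains possible.

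Third, eligibility in section 4.0 also covers willingness, so a subject unwilling to use NRT can enter through varenicline plus bupropion as well. This is correct, and it means that a clause on medical availability alone must come with a reworded reason. It does not weaken the point: a slow metabolizer who could take NRT and refuses it is a genuine negative for the Aim 2 measure.

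Finally, the effect is small. The pilot is descriptive and unpowered, broad eligibility suits a feasibility study, and choosing a denominator is often left to an analysis plan. The smallness stands. The protocol lists five forms, "NRT (i.e., patch, gum, lozenge, nasal spray, and inhalers"), and says "Nicotine replacement therapy is generally very safe (it is sold over the counter"), so medical ineligibility for NRT is probably uncommon. But the mismatch lies in the eligibility criterion itself, which an analysis plan does not set.

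**Conclusion.** The point holds. The criterion admits subjects in whom the NMR cannot guide the choice between classes, contrary to the reason given for it, and their fills still enter the Aim 2 measure. The textual mismatch is certain and needs no assumption. The numerical effect is minor: at most 4 points per affected subject and about 2 points near 50%, well inside the sampling error. Those sizes rest on 25 personalized-arm subjects, and the number affected is unknown. The case for a change rests on a clear inconsistency, a measure named in a primary analysis, and a very low cost of repair. The pilot's purpose adds to it, since its data are to inform the design of a full trial.

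**What to change.** Reconcile the criterion with its stated reason in one of two ways; the choice is for the investigators.

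1. **Change the criterion.** Add that the subject has no medical contraindication to at least one medication in each class, and align the opening words of the exclusion criteria with it. Reword the reason to say that the rule secures medical availability of both classes, not willingness. Cost: one clause in section 4.0 and a small, unknown loss of eligible subjects.
2. **Keep the criterion.** At the existing eligibility review, record who medically lacks an option in a class. Report the proportion filling the NMR-recommended prescription both overall and among subjects with both classes medically available. Reword the reason to say that the rule does not secure both classes for every subject. Cost: one recorded field and one extra proportion, with no loss of subjects.

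Under either option, keep subjects who merely decline NRT in the denominator.
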